5.2.6.2.2 AE reporting to the sponsor and timelines

The Investigator must report SAEs, AESIs, and non-serious AEs which are relevant for the reported SAE or AESI, on the BI SAE form via fax immediately (within 24 hours) to the sponsor's unique entry point (country specific contact details will be provided in the ISF). The same timeline applies if follow-up information becomes available. In specific occasions the Investigator could inform the sponsor upfront via telephone. This does not replace the requirement to complete and fax the BI SAE form.

With receipt of any further information to these events, a follow-up SAE form has to be provided. For follow-up information, the same rules and timeline apply as for initial information.

Proprietary confidential information © 2020 Boehringer Ingelheim International GmbH or one or more of its affiliated companies

5.2.6.2.3 Information required

All (S)AEs, including those persisting after the individual subject's end of trial, must be followed up until they have resolved, have been sufficiently assessed as 'chronic' or 'stable', or no further information can be obtained.

5.2.6.2.4 Pregnancy

Once the male subject has been enrolled in the clinical trial and has taken trial medication, and if a partner of the male trial participant becomes pregnant, the investigator must report any drug exposure during pregnancy in a partner of the male trial participant immediately (within 24 hours) by means of Part A of the Pregnancy Monitoring Form to the sponsor's unique entry point, after a written consent of the pregnant partner.

The outcome of the pregnancy associated with the drug exposure during pregnancy must be followed up and reported to the sponsor's unique entry point on the Pregnancy Monitoring Form for Clinical Trials (Part B).

The ISF will contain the Pregnancy Monitoring Form for Clinical Trials (Part A and Part B) as well as non-trial specific information and consent for the pregnant partner.

As pregnancy itself is not to be reported as an AE, in the absence of an accompanying SAE and/or AESI, only the Pregnancy Monitoring Form for Clinical Trials and not the SAE form is to be completed. If there is an SAE and/or AESI associated with the pregnancy, an SAE form must be completed in addition.

5.2.6.3 Collection and reporting of the adverse event headache

If the subject reports headaches during the treatment period the following information and data should be collected daily until the headache is resolved:

- Onset after medication intake (hhh:min)
- Headache severity on a Numeric Ranking Scale (NRS) ranging from 0 – 10
- Quality of headache (New type of headache vs. similar to previous experienced episodes of known headaches)
- Headache characteristics (pressing or tightening vs. burning vs. pulsating vs. aggravated by routine physical activity (such as walking or climbing stairs))
- Location (all of the following that apply: unilateral, bilateral, holocephal, frontal, temporal, occipital, facial)
- Any accompanying symptoms like (all of the following that apply: nausea and/or vomiting, photophobia, phonophobia, lacrimation, other)
- If Headache is resolved: Overall duration of headache episode (start time and end time)

5.3 DRUG CONCENTRATION MEASUREMENTS AND PHARMACOKINETICS

5.3.1 Assessment of pharmacokinetics

For the assessment of pharmacokinetics, blood samples will be collected at the time points indicated in the [Flow Chart](#). The actual sampling times will be recorded and used for determination of pharmacokinetic parameters.

5.3.2 Methods of sample collection

5.3.2.1 Blood sampling for pharmacokinetic analysis

[figure not shown]
For quantification of BI 1358894 concentrations in plasma, a blood sample will be drawn from an antecubital or forearm vein into an K₂-EDTA (dipotassium ethylenediaminetetraacetic acid)-anticoagulant blood drawing tube at the times indicated in the [Flow Chart](#). Blood will be withdrawn by means of either an indwelling venous catheter or by venepuncture with a metal needle.

For quantification of [C-14] BI 13588945 plasma concentrations, an additional K2-EDTA tube needs to be collected as indicated in the [Flow Chart](#). Blood will be withdrawn by means of either an indwelling venous catheter or by venipuncture with a metal needle.

For detailed description of blood sampling, sample handling, sample preparation, sample storage, tube labelling and sample shipment please refer to the laboratory manual.

At a minimum, the sample tube labels should list BI trial number, subject number, and planned sampling time.

After completion of the trial, the plasma samples may be used for further methodological investigations (e.g. for stability testing or assessment of metabolites. However, only data related to the analyte and/or its metabolite(s) including anti-drug antibodies (if applicable) will be generated by these additional investigations. The study samples will be discarded after completion of the additional investigations but not later than 5 years after the CTR is archived.

5.3.4 Pharmacokinetic - pharmacodynamic relationship

No analysis of the relationship between pharmacokinetic and pharmacodynamic parameters is planned for this trial.

5.4 ASSESSMENT OF BIOMARKER(S)

Not applicable.

5.5 BIOBANKING

Not applicable.

5.6 APPROPRIATENESS OF MEASUREMENTS

All measurements performed during this trial are standard measurements and will be performed in order to monitor subjects' safety and to determine pharmacokinetic parameters in an appropriate way. The scheduled measurements will allow monitoring of changes in vital signs, standard laboratory values, and ECG parameters that might occur as a result of administration of trial medication. The safety assessments are standard, are accepted for evaluation of safety and tolerability of an orally administered drug, and are widely used in clinical trials. The pharmacokinetic parameters and measurements outlined in Section [5.4](#) are generally used assessments of drug exposure.

6. INVESTIGATIONAL PLAN

6.1 VISIT SCHEDULE

Exact times of measurements outside the permitted time windows will be documented. The acceptable time windows for screening and the end of trial examination are provided in the [Flow Chart](#).

Study measurements and assessments scheduled to occur 'before' trial medication administration on Day 1 of each treatment period are to be performed and completed within a 2 h-period prior to the trial drug administration.

The acceptable deviation from the scheduled time for vital signs, ECG, and laboratory tests will be \pm 10 min for the first 4 h following the trial drug administration (on Day 1 of each treatment period) and \pm 30 min thereafter until discharge on Day 5. During the ambulatory visits, the acceptable deviation from the scheduled time for vital signs, ECG, and laboratory tests will be \pm 120 min.

If scheduled in the [Flow Chart](#) at the same time as a meal, blood sampling, vital signs, and 12-lead ECG recordings have to be done first. Furthermore, if several measurements including venepuncture are scheduled for the same time, venepuncture should be the last of the measurements due to its inconvenience to the subject and possible influence on physiological parameters.

For planned blood sampling times, refer to the [Flow Chart](#). While these nominal times should be adhered to as closely as possible, the actual sampling times will be recorded and used for the determination of pharmacokinetic parameters.

If a subject misses an appointment, it will be rescheduled if possible. The relevance of measurements outside the permitted time windows will be assessed no later than at the Report Planning Meeting.

6.2 DETAILS OF TRIAL PROCEDURES AT SELECTED VISITS

6.2.1 Screening period

After having been informed about the trial, all subjects will provide written informed consent in accordance with GCP and local legislation prior to enrolment in the study.

For information regarding laboratory tests (including drug and virus screening), ECG, vital signs, and physical examination, refer to Sections [5.2.3](#) to [5.2.5](#).

6.2.2 Treatment periods

Each subject is expected to participate in 3 treatment periods (Part 1 of the trial and Period 2 and 3 of Part 2). At least 17 days will separate drug administrations in the first and second Part of the trial as well as in the second and third treatment periods of Part 2 of the trial.

On Day – 1 of each treatment period, study participants will be admitted to the trial site and kept under close medical surveillance for at least 96 h following drug administration. The

Proprietary confidential information © 2020 Boehringer Ingelheim International GmbH or one or more of its affiliated companies

subjects will then be allowed to leave the trial site after formal assessment and confirmation of their fitness. On all other study days, subjects will be treated in an ambulatory fashion.

For details on time points and procedures for collection of plasma samples for PK analysis, refer to [Flow Chart](#) and Section [5.3.2](#).

The safety measurements performed during the treatment period are specified in Section [5.3](#) of this protocol and in the [Flow Chart](#). For details on times of all other trial procedures, refer to the [Flow Chart](#). AEs and concomitant therapy will be assessed continuously from screening until the end of trial examination.

6.2.3 Follow-up period and trial completion

For AE assessment, laboratory tests, recording of ECG and vital signs, and physical examination during the follow-up period, see Sections [5.2.2](#) to [5.2.5](#).

Subjects who discontinue treatment before the end of the planned treatment period should undergo the EoTrial Visit.

All abnormal values (including laboratory parameters) that are assessed as clinically relevant by the investigator will be monitored using the appropriate tests until a return to a medically acceptable level is achieved. (S)AEs persisting after a subject's EoTrial Visit must be followed until they have resolved, have been sufficiently characterised, or no further information can be obtained.

7. STATISTICAL METHODS AND DETERMINATION OF SAMPLE SIZE

[figure not shown]
7.1 STATISTICAL DESIGN – MODEL

Part 1:

The main objective of this study part 1 is to investigate absolute bioavailability of an unlabelled oral tablet formulation of BI 1358894 (Test 1, T1) compared to BI 1358894 [C-14] as intravenous solution (Reverence 1, R1) in healthy male subjects on the basis of the primary and secondary pharmacokinetic endpoints, as listed in Section [2.1.2](#) and [2.1.3](#).

Part 2:

The main objective of this study part 2 is to investigate the relative bioavailability of 100 mg BI 1358894 administered as an oral suspension in fed healthy male subjects (Test 2, T2) compared with 100 mg BI 1358894 administered as an oral suspension in fasted healthy male subjects (Reverence 2, R2) on the basis of the primary and secondary pharmacokinetic endpoints, as listed in Section [2.1.2](#) and [2.1.3](#).

The trial is designed to allow intra-subject comparisons and will be evaluated statistically by use of a linear model for logarithmically transformed PK endpoints.

The assessment of safety and tolerability is a further objective of this trial, and will be evaluated by descriptive statistics for the parameters specified in Section [2.2.2.2](#).

7.2 NULL AND ALTERNATIVE HYPOTHESES

Part 1:

The absolute bioavailability of 100 mg BI 1358894 with an intravenous microdose formulation containing labelled [C-14] BI 1358894 compared with an unlabelled oral tablet formulation of BI 1358894 will be estimated by the ratios of the geometric means (test/reference), and their corresponding 2-sided 90% confidence intervals (CIs) will be provided. This method corresponds to the two one-sided t-test procedure, each at the 5% significance level. Since the main focus is on estimation and not testing, a formal hypothesis test and associated acceptance range is not specified.

Part 2:

The relative bioavailability of 100 mg BI 1358894 administered as an oral suspension under fed conditions compared with 100 mg BI 1358894 administered as an oral suspension under fasted conditions will be estimated by the ratios of the geometric means (test/reference), and their corresponding 2-sided 90% confidence intervals (CIs) will be provided. This method corresponds to the two one-sided t-test procedure, each at the 5% significance level. Since the main focus is on estimation and not testing, a formal hypothesis test and associated acceptance range is not specified.

In both parts of the trial, confidence intervals and p-values will be computed, but have to be interpreted in the perspective of the exploratory character of the study, i.e. confidence intervals are considered as interval estimates for effects, while p-values are considered as an exploratory measure of evidence for effects in the present data.

7.3 PLANNED ANALYSES

Analysis sets

Statistical analyses will be based on the following analysis sets:

- Treated set (TS): The treated set includes all subjects who were randomized and treated with at least one dose of study drug. The treated set will be used for safety analyses.
- Pharmacokinetic parameter analysis set (PKS): This set includes all subjects in the treated set (TS) who provide at least one PK endpoint that was defined as primary or secondary and was not excluded due to a protocol violation relevant to the evaluation of PK or due to PK non-evaluability (as specified in the following subsection 'Pharmacokinetics'). Thus, a subject will be included in the PKS, even if he contributes only one PK parameter value for one period to the statistical assessment. Descriptive and model based analyses of PK parameters will be based on the PKS.

Adherence to the protocol will be assessed by the trial team. Important protocol violation (IPD) categories will be suggested in the IQRM plan, IPDs will be identified no later than in the Report Planning Meeting, and the IPD categories will be updated as needed.

Pharmacokinetics

The pharmacokinetic parameters listed in Section [2.1](#) for drug BI 1358894 will be calculated according to the relevant SOP of the Sponsor ([001-MCS-36-472](#)).

Plasma concentration data and parameters of a subject will be included in the statistical pharmacokinetic (PK) analyses if they are not flagged for exclusion due to a protocol violation relevant to the evaluation of PK (to be decided no later than in the Report Planning Meeting) or due to PK non-evaluability (as revealed during data analysis, based on the criteria specified below). Exclusion of a subject's data will be documented in the CTR.

Relevant protocol violations may be:

Proprietary confidential information © 2020 Boehringer Ingelheim International GmbH or one or more of its affiliated companies

- Incorrect trial medication taken, i.e. the subject received at least one dose of trial medication the subject was not assigned to
- Incorrect dose of trial medication taken
- Use of restricted medications

Plasma concentrations and/or parameters of a subject will be considered as non-evaluable, if for example

- The subject experienced emesis that occurred at or before two times median t_{max} of the respective treatment (Median t_{max} is to be determined excluding the subjects experiencing emesis),
- A predose concentration is $>5\%$ C_{max} value of that subject
- Missing samples/concentration data at important phases of PK disposition curve

Plasma concentration data and parameters of a subject which is flagged for exclusion will be reported with its individual values but will not be included in the statistical analyses. Descriptive and inferential statistics of PK parameters will be based on the PKS.

Only concentration values within the validated concentration range and actual sampling times will be used for the calculation of pharmacokinetic parameters. Concentrations used in the pharmacokinetic calculations will be in the same format provided in the bioanalytical report, (that is, to the same number of decimal places provided in the bioanalytical report).

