3. DESCRIPTION OF DESIGN AND TRIAL POPULATION

3.1 OVERALL TRIAL DESIGN AND PLAN

Part 1 of the study will be performed as a non-randomised, open-label trial in healthy male subjects in order to investigate the pharmacokinetics and absolute bioavailability of BI 1358894 as an oral tablet co-administered with an i.v. microtracer dose of [C-14]-BI 1358894. The reference treatment in Part 1 (Reference 1 – R1) will be 10 mL intravenous infusion of 100 µg BI 1358894 using a mixture of 90 µg unlabelled and 10 µg [C-14] labelled BI 1358894. The oral treatment (Test 1 – T1) will consist of two 50 mg BI 1358894 tablets administered on Day 1 to subjects in the fasting state. The i.v. infusion will start 5 hours after oral drug administration, i.e. at the time of the expected t_{max} .

This will be followed by Part 2 of the study which will be performed as a randomised, open-label, single-dose, two-period, two-sequence cross-over trial to investigate the relative bioavailability of BI 1358894 administered as an oral suspension. In Part 2, the treatments will consist of a single dose of 100 mg BI 1358894 administered as an oral suspension either in the fasted state (Reference 2 – R2) or in the fed state (Test 2 – T2). In Part 2, the subjects will be randomly allocated to the 2 treatment sequences (T2-R2 or R2-T2).

Part 1 and Part 2 are designed in a fixed sequence.

For details, refer to Section [4.1](#).

There will be a washout period of at least 17 days between the treatments, i.e. the dosing in Part 1 and the dosing in the first treatment period of Part 2, as well as the dosing in the first treatment period of Part 2 and the dosing in the second treatment period of Part 2 are separated by at least 17 days.

An overview of all relevant trial activities is provided in the [Flow Chart](#). For visit schedule and details of trial procedures at selected visits, refer to Sections [6.1](#) and [6.2](#), respectively.

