4.1.3 Method of assigning subjects to treatment groups

Part 1 of the trial is open-labelled, single arm, therefore all subjects will receive the same treatments. Each subject will be assigned a subject number prior to dosing on Day 1 of Visit 2.

Part 1 and Part 2 will be conducted in a fixed-sequence design.

Part 2 of the trial follows a randomized, two-treatment, two-sequence study design. The randomisation list for Part 2 will be provided to the trial site in advance.

Subjects will be allocated to treatment sequences prior to the administration of trial medication in the morning of Day 1 (Visit 3). For this purpose, numbers of the randomisation list will be allocated to the subjects in order of screening (the subject who was screened and approved first will be the first subject on the subject list). Subjects are then assigned to a treatment sequence according to the randomisation list.

Once a subject number has been assigned, it cannot be reassigned to any other subject.

The randomisation procedure is described in Section [7.6](#).

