7.3.4 Safety analyses

Safety will be analysed based on the assessments described in Section [2.2.2.2](#). All treated subjects (TS, refer to Section [7.2](#)) will be included in the safety analysis. Safety analyses will be descriptive in nature and based on BI standards. No hypothesis testing is planned.

For all analyses, the treatment actually administered (= treatment at onset) to the subject will be used (any deviations from the randomised treatment will be discussed in the minutes of the Report Planning Meeting).

Treatments will be compared in a descriptive way. Tabulations of frequencies/proportions will be used to evaluate categorical (qualitative) data, and tabulations of descriptive statistics will be used to analyse continuous (quantitative) data.

Measurements (such as ECG, vital signs, or laboratory parameters) or AEs will be assigned to treatments (see Section [4.1](#)) based on the actual treatment at the planned time of the measurement or on the recorded time of AE onset (concept of treatment emergent AEs). Therefore, measurements planned or AEs recorded prior to first intake of trial medication will be assigned to the screening period, those between first trial medication intake (test

Proprietary confidential information © 2020 Boehringer Ingelheim International GmbH or one or more of its affiliated companies

treatment) and beginning of reference treatment will be assigned to the test treatment period. Those between the start of infusion until the end of REP (see Section [1.2.2](#)) will be assigned to the combined test/reference treatment period. Events occurring after the REP but prior to next intake or end of trial termination date will be assigned to 'follow-up'. These assignments including the corresponding time intervals will be defined in detail in the TSAP. Note that AEs occurring after the last per protocol contact but entered before final database lock will be reported to Pharmacovigilance only and will not be captured in the trial database.

Additionally, further treatment intervals (analysing treatments) may be defined in the TSAP in order to provide summary statistics for time intervals, such as combined treatments, on-treatment totals, or periods without treatment effects (such as screening and follow-up intervals).

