7.6 RANDOMISATION

Part 1:

Randomization is not applicable in this open-label and single group clinical study part. All subjects will receive the same treatment. Consecutive subject numbers will be assigned via the EDC system.

Part 2:

Subjects will be randomised to one of the 2 treatment sequences in a 1:1 ratio. The block size will be documented in the CTR.

The sponsor will arrange for the randomisation as well as packaging and labelling of trial medication. The randomisation list will be generated using a validated system that uses a pseudo-random number generator and a supplied seed number so that the resulting allocation is both reproducible and non-predictable.

The randomisation list will contain additional blocks to allow for subject replacement (refer to Section [3.3.5](#)).

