Proprietary confidential information © 2020 Boehringer Ingelheim International GmbH or one or more of its affiliated companies

- Repeated nasopharyngeal PCR test at follow-up visit.
- Physical exams will be limited to the necessary visits (screening, discharge and follow-up).
- In cases where subjects are not able to attend study visits due to the presence of a SARS-CoV 2 infection, the Investigator will discuss with the Sponsor potential mitigation approaches (including, but not limited to, extending the visit window, conducting evaluations via video link or phone call, allowing for safety procedures to be conducted at a local facility). The rationale (e.g., the specific limitation imposed by the SARS-CoV-2 infection that led to the inability to perform the protocol-specified assessment) and outcome of the discussion will be documented in the electronic case report form (eCRF).
- A subject should not be admitted if there was any contact with a COVID-19 patient within the last 2 weeks prior to admission to the clinical research unit.
- If a subject is tested to be SARS-CoV-2 positive on Day -1, the subject will be excluded from participation with reference to exclusion criterion #4, and referred for treatment.
- If a subject becomes ill and/or is tested to be SARS-CoV-2 positive after the first administration of study treatment, dosing will be stopped. The subject will be isolated from other study participants and referred for treatment. The subject will be followed up in quarantine in the clinical research unit until complete elimination of the study compound or will be asked to quarantine at home according to guidelines of the Dutch government.

Conclusion of COVID-19 risk containment

Given the profile of the compound and given the study design, the COVID-19 risk minimization strategy as summarized above is considered adequate. The BI trial team and the ██████████ Principal Investigator and supporting staff recommend study continuation as per latest version of the protocol and with implementation of the measures detailed in this appendix to the protocol.

Proprietary confidential information © 2020 Boehringer Ingelheim International GmbH or one or more of its affiliated companies

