#### **4. CHANGES IN THE PLANNED ANALYSIS OF THE STUDY**

All analyses described in this TSAP are in accordance with the statistical methods planned in the revised CTP.

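### The treated set requires randomisation, so a subject dosed in Part 1 who leaves before Visit 3 allocation falls out of the safety and PK analysis sets

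*Protocol*

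**What the plan says.** Protocol 7.3 sets two conditions for the TS: "The treated set includes all subjects who were randomized and treated with at least one dose of study drug". SAP 6.3 repeats the sentence, and SAP section 4 reports no departure: "All analyses described in this TSAP are in accordance with the statistical methods planned in the revised CTP".

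The other sets are nested in the TS. For the PKS: "This set includes all subjects in the treated set (TS) who provide at least one PK endpoint that was defined as primary or secondary". The ECG plasma concentration set (ECGPCS), added in SAP 6.3, is also drawn from the TS. SAP Table 6.3: 1 puts disposition, important protocol deviations, demographics, exposure and safety on the TS, and the primary and secondary PK endpoints on the PKS.

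On randomisation in Part 1, Protocol 7.6 says: "Randomization is not applicable in this open-label and single group clinical study part". For Part 2, Protocol 4.1.3 says: "Subjects will be allocated to treatment sequences prior to the administration of trial medication in the morning of Day 1 (Visit 3"). The Part 2 flow chart places this step one hour before dosing. Protocol 3.1 fixes the spacing, "There will be a washout period of at least 17 days between the treatments", and applies it explicitly to the gap between Part 1 dosing and the first Part 2 dosing.

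Protocol 7.3.4 describes the safety population differently: "All treated subjects (TS, refer to Section [7.2](#)) will be included in the safety analysis". (The section cited there is wrong; the definition is in 7.3.)

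**The concern.** All Part 1 exposure comes before the only randomisation in the trial. Taken literally, the TS is the set of subjects who reached Part 2 allocation, not the set who received drug. Anyone dosed in Part 1 who leaves earlier would be missing from every TS summary (disposition, exposure, adverse events, laboratory, vital signs, ECG) and from the Part 1 absolute bioavailability analysis.

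Leaving early need not be unrelated to safety. The discontinuation reasons in Protocol 3.3.4.1 include adverse events, raised CRP, liver criteria and serious adverse reactions, so the wording can remove the very subjects a safety set should hold. In the limiting case, Protocol 3.3.4.3 provides for ending the trial after one drug-related serious adverse event. If that happened in Part 1 before anyone was allocated, the TS as written would be empty although subjects had been exposed.

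**Working it through.** **1. Membership under the written rule**

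| Subject | Dosed | Randomised | TS | PKS / ECGPCS |
|---|---|---|---|---|
| Leaves after Visit 3 allocation | yes | yes | in | eligible |
| Dosed in Part 1, leaves before allocation | yes | no | out | out |

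Neither document places randomisation earlier or defines a separate Part 1 treated set.

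**2. Timing, in hours from the Part 1 oral dose**

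- Earliest first Part 2 dose: 17 × 24 = 408 h.
- Allocation, one hour earlier: 407 h.
- Period 2 admission, at -22 h: 408 − 22 = 386 h.
- Last Part 1 PK sample: 312 h.
- End of the Part 1 on-treatment phase (SAP Table 6.1: 1): end of infusion at 5.25 h plus 11 × 24 = 264 h gives 269.25 h.

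The Part 1 on-treatment phase and all Part 1 PK sampling are therefore over before any subject can be randomised. A subject can have complete Part 1 data and still not qualify.

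**3. A route the documents themselves provide**

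Protocol Appendix 10.2 schedules a PCR test at admission on Day -1 of each period. For a subject who "is tested to be SARS-CoV-2 positive after the first administration of study treatment, dosing will be stopped". A separate bullet excludes subjects who test positive on Day -1. At Period 2 admission (386 h at the earliest), either bullet leaves the subject unallocated unless the visit is postponed, and all his Part 1 samples were due by 312 h.

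**4. Size in the safety tables**

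One such subject is 1/12 = 8.3% of those exposed, or 1/13 = 7.7% if he is replaced under Protocol 3.3.5. If he had the only case of an event, the TS table would show 0/11 instead of 1/12.

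**5. Size in Part 1 precision**

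Precision is upper confidence limit/estimate, expected with 95% probability (Protocol 7.7):

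precision = exp[ t(0.95, df) × s_w × √(2/N) × √(χ²(0.95, df)/df) ], with s_w = √ln(1 + gCV²).

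*Check against the plan.* For the 2×2 crossover, df = N − 2. With N = 12 and gCV 18%: t = 1.8125, s_w = 0.17857, √(2/12) = 0.40825, √(18.307/10) = 1.35304. The exponent is 0.17877 and the precision 1.1958; Table 7.7: 2 gives 1.196. With N = 10 the formula gives 1.2297; Table 7.7: 1 gives 1.230.

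*Part 1.* The model has subject and formulation only, so df = N − 1. With N = 12 and gCV 8%: t = 1.7959, s_w = 0.07987, √(2/12) = 0.40825, √(19.675/11) = 1.33740. The exponent is 0.07832 and the precision 1.0815. Likewise:

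| Evaluable N in Part 1 | df | gCV 8% | gCV 18% |
|---|---|---|---|
| 12 | 11 | 1.0815 | 1.1914 |
| 11 | 10 | 1.0871 | 1.2053 |
| 10 | 9 | 1.0939 | 1.2223 |

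Protocol 7.7 gives 8% for AUC0-∞ and 18% for Cmax, both from an earlier oral trial. That this range carries over to the oral/i.v. comparison is an assumption. The rows for 11 and 10 assume one or two losses without replacement.

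**The case against.** The strongest reply is that the intent is plain and the phrase is a leftover. Protocol 7.3.4 speaks of all treated subjects. The PKS text accepts a single parameter from a single period. SAP Table 6.1: 1 defines Part 1 on-treatment phases that run before any randomisation. In SAP Table 6.2: 1 the only deviation that removes a subject from the TS is missing consent. Exclusions are settled by the Report Planning Meeting, where such a case would surface. The intent is indeed clear, but that shows a contradiction and does not remove it: the definition is what gets programmed. Settling the matter at that meeting would mean deciding who counts as treated with the data in view.

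Second, the effect is conditional and the infection route is not certain. Appendix 10.2 allows visit windows to be extended, and the washout has no stated maximum, so a positive test need not end participation. That stands. It lowers the likelihood of this one route and leaves the other reasons for leaving early.

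Third, the harm is limited. Protocol 3.3.4 and SAP 6.6 require a dosed subject's data to be reported, SAP section 7 lists all individual values, safety analyses are descriptive, and with an evaluable replacement Part 1 stays at 12 even under the literal rule. This also stands. The loss is from summaries and models, not from all reporting, and the PK effect is minor.

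Finally, two other SAP items do not fit a Part 1-only subject. The Part 1 follow-up phase in Table 6.1: 1 ends only at first Part 2 dosing, and listings sort by full sequence. Neither blocks the correction: the Part 1 on-treatment phases do not depend on Part 2, and the summary AE displays show on-treatment phases only.

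**Conclusion.** The concern holds. As written, a subject dosed in Part 1 who leaves before Visit 3 allocation is outside the TS, the PKS and the ECGPCS, contrary to Protocol 7.3.4. Subjects who leave after allocation are unaffected, and nothing changes if all 12 reach it.

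How often this would happen cannot be judged, because no dropout rate is given. Per subject it costs 8.3% of the exposed population in the safety summaries. For Part 1 AUC0-∞, one unreplaced loss moves precision from 1.0815 to 1.0871 at gCV 8%, or from 1.1914 to 1.2053 at 18%, which is negligible for an estimation trial with no acceptance range. The point should be fixed because a safety set must contain everyone exposed; it does not threaten the primary result.

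**What to change.** In SAP 6.3, delete *randomized and* from the TS definition, so that membership depends only on having received at least one dose of study drug (tablet, C-14 infusion or suspension). Record this in SAP section 4 as a change from the protocol, and add a history-table row. Align Protocol 7.3 when the protocol is next amended; this point alone does not call for an amendment.

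The PKS and ECGPCS definitions, the sample size and both models stay as they are. The cost is a short SAP revision before database lock, with no operational consequence. The same revision could usefully give the Part 1 follow-up phase a trial-termination end point and say where a subject without a sequence appears in the listings, but the correction does not depend on either.
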